**Multicenter: University of Michigan ([name])**

**INSTRUCTIONS**

This template is intended to help investigators prepare a protocol that includes all of the necessary information needed by the IRB to determine whether a study meets approval criteria. **Read the following instructions before proceeding:**

1. Use this protocol template for a PI initiated study that includes direct interactions with research subjects. Additional templates for other types of research protocols are available in the system Library.
2. If a section or question does not apply to your research study, type “Not Applicable” underneath.
3. Once completed, upload your protocol in the “Basic Information” screen in IRES IRB system.

**SECTION I: RESEARCH PLAN****Section 1. Statement of Purpose:** State the scientific aim(s) of the study, or the hypotheses to be tested.

The coronavirus disease-19 (COVID-19) pandemic has caused significant distress, and grief around the world. Given the rising numbers of infected individuals in the United States (US) and need for hospitalization in at least 14% of infected patients (1), there is substantial strain on the health care system. Identifying ways to ameliorate the progression and severity of this infection and preventing hospitalization is critical in preventing break in capacity and overwhelming the healthcare system.

Currently, it is believed that COVID-19 infected patients undergo two phases of illness; viral replication and the more fatal phase of inflammation. Preventing the inflammatory phase has the potential to decrease hospitalization, use of ventilation and mortality. Accordingly, we are proposing to identify the role of resistant potato starch (a natural dietary supplement) in preventing the progression to the inflammatory phase through its immunomodulatory effects on the gut microbiome.

To enhance generalizability, we have designed a multicenter study in varying geographical regions within the US, involving patients who tested positive and are not in need of hospitalization. Using a randomized phase III clinical trial design, we will enroll 1500 COVID-19 positive patients who are not hospitalized, to be randomized to receiving 2 tablespoons (~20 grams) of resistant potato starch (RPS) twice daily for 14 days vs. placebo (2 tablespoons of non-resistant, digestible starch twice daily). We will evaluate the relationship between RPS and the primary outcome of hospitalization and the secondary outcomes of time to clinical recovery (TTCR) defined as return to normal body temperature, and alleviation of major presenting symptoms (myalgia, cough, shortness of breath, and GI symptoms) maintained for 72 hours and peak symptom severity score adapted from the influenza literature (2).

The dietary starch produced by Bob's Red Mill® is a commercially available low-digestible carbohydrate. It is entirely plant based and not genetically modified. It is gluten free. Potato-based starch contains 40 calories per 12 grams and no additional dietary nutrients, vitamins or sodium (labeling information). Corn-based starch contains 30 calories per 8 grams and no additional nutrients, vitamins or sodium (labeling information).

[figure not shown]
Starch has been well studied within the dietary and nutritional literature and has been demonstrated safe. (3-5). In addition, it has previously been administered to healthy human volunteers at the University of Michigan as part of HUM00118951 and HUM00094242– Linking the Structure and Function of the Gut Microbiome. These studies have revealed minimal adverse events and no serious adverse events in these subjects.

Moreover, it is being administered to allogeneic hematopoietic cell transplant (allo HCT) patients at the University of Michigan as part of HUM00112318 under IND 132208- Dietary manipulation of the microbiome-metabolomic axis for mitigating graft versus host disease (GVHD) in allo HCT patients. This study has revealed minimal adverse events and no serious adverse events in these subjects.

**Probable Duration of Project:** State the expected duration of the project, including all follow-up and data analysis activities. We anticipate a 12-month study duration, whereby the first six months will focus on RPS administration and data collection and the remaining six months on analysis and manuscript generation.

**Section 2. Background:** Patients suffering from COVID-19 have been shown to have significant inflammation resembling cytokine release syndrome (CRS) (6). It is thought that this inflammatory phase persisting even after viral suppression is what leads to the more fatal phase of COVID-19.(7,8). One of the most commonly elevated markers in COVID-19 patients has been shown to be interleukin (IL)-6.(6,7). To this effect an IL-6 inhibitor known as Tocilizumab, usually used in the treatment of inflammatory conditions including CRS, has been used to help modulate and reduce this exaggerated inflammatory response in COVID-19 patients (9). Tocilizumab is mainly used and studied in hospitalized patients who are showing signs of increased inflammation, but more research on interventions to slow the onset of inflammation and decrease hospitalizations in COVID-19 patients is needed. **Towards this effort, we propose to study the effects of RPS on the rate of hospitalizations in COVID-19 patients who have not yet required hospitalization.** Decreasing hospitalization rates is vital in preventing the current burden on our healthcare system and will minimize exposure of healthcare workers to this highly infectious disease. The rationale for using RPS to mitigate COVID-19 hospitalizations is based on the ability of resistant starch to decrease IL-6 in humans (Figure 1).(10,11). Furthermore, others, as well as our group, have shown that resistant starch increases butyrate levels (12-14), which in turn has been shown to reduce IL-6 production and overall inflammation (15). Additionally butyrate has also been shown to specifically decrease lung inflammation in animal models by suppressing inflammatory cytokine production (Figure 2) (16-20). As butyrate is produced in higher amounts in the gastrointestinal tract, it can be absorbed into the bloodstream and has been shown to have significant amelioration of lower respiratory infections and inflammation in humans (21). It

has also been postulated that butyrate decreases Angiotensin Converting Enzyme 2 (ACE2) receptor expression, which is the main entry mechanism for COVID-19 into epithelial lung cells (16-19). Our preliminary data shows that within one week of being on RPS therapy (~20 grams twice daily), participants' stool butyrate levels increases (14). As RPS is a commonly used nutritional supplement, often used in gluten free cooking and baking, it offers minimal risk to participants in this proposed work. Furthermore, we have encountered only minimal adverse events and no serious adverse events from its use in our preliminary data in allo HCT patients (HUM00112318 under IND 132208) (14). Hence, we propose to enroll 1500 COVID-19 positive patients, who are being monitored in the outpatient setting, to receive 2 tablespoons (~ 20 grams) of RPS twice daily for 14 days vs. placebo to test **our hypothesis that RPS will reduce rate of hospitalization in COVID-19 patients**. Our primary outcome of interest will be rate of hospitalization for COVID-19 related complications and our secondary outcomes will be TTCA and symptom severity score (2). If our hypothesis is proven, this simple, minimal risk intervention, will have the potential to reduce healthcare burden and improve patient outcomes.

[figure not shown]

**Figure 2.** Schematic of the effect of RPS on lung inflammation

complications and our secondary outcomes will be TTCA and symptom

[figure not shown]
severity score (2). If our hypothesis is proven, this simple, minimal risk intervention, will have the potential to reduce healthcare burden and improve patient outcomes.

**Figure 1.** Schematic of the effect of RPS on lowering IL-6

[figure not shown]
### Section 3. Preliminary Data

• **RPS is potent at increasing butyrate levels in stool of healthy humans, compared to other forms of dietary resistant starch.** Published data showed that administration of defined quantities of RPS induces production of butyrate from the microbiota in 20 healthy volunteers (12) (Figure 3).

[figure not shown]

**Figure 3.** Fecal butyrate levels before (blue) and after (red) RPS (“Potato”) or other commercially available dietary resistant starch preparations

• **RPS alters stool butyrate levels in allo HCT patients.** Our published preliminary data showed that administration of RPS in a pilot study increased stool butyrate levels in allo HCT recipients (14) (Figure 4).

[figure not shown]

**Figure 4.** Effect of RPS on allo HCT recipients' stool butyrate levels.

**Figure 5.** Effects of butyrate on IL-6 release. (A-F) The effects of butyrate on IL-6 release with 24 h pre-incubation and 6, 12, or 24 h stimulation. (A-C) Butyrate combined with LPS. (D-E) Butyrate combined with TNF $\alpha$ . N = 4, \*\*p < 0.01, \*\*\*p < 0.001 compared with control group. #p < 0.05, ##p < 0.01, ###p < 0.001 compared with LPS or TNF $\alpha$  group.

• **Butyrate is associated with less viral lower respiratory tract infections.** Increased abundance of butyrate producers in the intestinal microbiome (which is correlated with higher stool butyrate levels) was associated with less viral lower respiratory tract infections in allo HCT recipients (21) (**Figure 6**)

[figure not shown]
**Figure 6.** Increased butyrate producers are associated with reduction in viral lower respiratory tract infections

#### Section 4. Research Plan:

##### Study Design.

This is a multicenter phase III randomized, placebo controlled, double blinded, clinical trial enrolling 1500 COVID-19 positive patients who are being managed as outpatients to investigate the role of RPS in incident hospitalization after COVID-19 diagnosis as well as the secondary outcomes of TTTR and symptom severity score. Participants will be enrolled from multiple sites. Patients will be identified via Electronic Health Record (EHR) using a real time compiled list of COVID-19 positive patients at University of Michigan, and will similarly be identified via an EHR compiled list at other sites. Initial screening will be conducted via review of the EHR and will be followed up by a telephone call to obtain informed consent and to confirm inclusion and exclusion criteria (**Table 1**). If subjects agree to participate in the study via phone and meet the inclusion criteria, an informed consent document will be sent to patients electronically for subjects to sign digitally via SignNow. Upon receipt of subject's informed consent documentation with approval to participate in our study, pre-packaged Bob's Red Mill® RPS vs. pre-packaged placebo consisting of iso-caloric digestible Bob's Red Mill® corn starch (non-resistant starch) will be delivered to their home, with printed instructions (see

**Figure 7. Trial Design**

**attached instructions**) on how to take the RPS or placebo for the duration of the trial. Patients will be asked to take 2 tablespoons (~20 grams) of RPS in water or juice or applesauce (any cool substance to make it palatable) twice daily for 14 days with the same instructions for the placebo arm. Patients will be called every 2 days while taking RPS to assess symptoms and adverse events via a pre-specified questionnaire (**see attached questionnaire**) for the first 14 days and then will be called weekly until 30 days after the last dose of treatment. Patients are then followed via EHR to complete the 4-months follow up from the time of diagnosis (ie. COVID test positive) (**Figure 7**). Of note, the placebo will be identical in appearance and packaging as the RPS. Both food ingredients, placebo and RPS, are isocaloric (approximately 140 calories per day from either food ingredient). The placebo has been safely used as a control in human clinical trials (NCT 02763033, NCT01939600, NCT01708694).

**Inclusion and Exclusion Criteria:**

**Table 1.** Inclusion and Exclusion criteria:

|                    |  |
|--------------------|--|
| Inclusion criteria | Participants >18 years of age with COVID-19 positive status who are monitored in the outpatient setting and are English speaking.  |
| Exclusion criteria | Inflammatory bowel disease, history of gastric bypass surgery, active Clostridium difficile infection, active participation in another COVID-19 intervention trial, any physical or psychological condition that, in the opinion of the investigator, would pose unacceptable risk to the patient or raise concern that the patient would not comply with protocol procedures. We will also exclude reported allergy to potato starch or corn starch or difficulty swallowing in order to prevent any aspiration risk or anyone on IL-6 inhibitors (such as Tocilizumab) |

**Primary Objectives**

-To assess the effect of RPS on hospitalization rates in COVID-19 infection

**Primary Outcome Measure:**

Hospitalization for a COVID-19 related admission during the first month of follow up.

A COVID-19 related admission is defined as the following:

- Presenting symptoms of fever or shortness of breath or myalgia or cough or hypoxia.
- Admission diagnosis of hypoxic respiratory failure, pneumonia, viral pneumonia.
- Death prior to hospitalization thought to be secondary to COVID-19 will also be defined as an event.

All hospital admissions will be reviewed and adjudicated by site PI to ensure that the hospitalization is a COVID-19 related admission.

**Secondary Objectives**

-To access the effect of RPS on time to clinical recovery (TTCR)

**Secondary Outcome Measure:**

TTCR will be defined as a return to normal body temperature to 97°F -99°F as reported by the patient, and resolution of any major presenting symptoms (myalgia, cough, shortness of breath, GI symptoms) maintained for 72 hours.

-To assess the effect of RPS on symptom severity score

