**A. Over the past 2-3 days:**

|  | Absent | Mild | Moderate | Severe |
|--|--------|------|----------|--------|
| 1) Do you have loss of taste or smell?                       |        |      |          |        |
| 2) Do you have any bellyaches, diarrhea, or nausea/vomiting? |        |      |          |        |
| 3) Do you have a cough?                                      |        |      |          |        |
| 4) Are you short of breath or wheezy on rest or exertion?    |        |      |          |        |
| 5) Do you have a fever or feel feverish?                     |        |      |          |        |
| 6) Are you experiencing fatigue?                             |        |      |          |        |
| 7) Do you have a headache?                                   |        |      |          |        |
| 8) Do you have muscle aches, pains, or cramps?               |        |      |          |        |

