**B. What medication are you on currently?**

| Name of drug | Dose | Frequency | Newly started within the past 2-3 days (Y/N) |
|--------------|------|-----------|--|
|              |      |           |  |
|              |      |           |  |

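### TTCR sets no condition on fever-reducing or pain-relieving drugs, so drug-suppressed fever or myalgia can count as recovery; the current-drug data from the call script are not used

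*Combined protocol and SAP*

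**What the plan says.** Under Secondary Objectives, the endpoint requires a temperature back in the 97–99°F range "as reported by the patient, and resolution of any major presenting symptoms (myalgia, cough, shortness of breath, GI symptoms) maintained for 72 hours". The shorter definition in Section 1 (Statement of Purpose) is "return to normal body temperature, and alleviation of major presenting symptoms (myalgia, cough, shortness of breath, and GI symptoms) maintained for 72 hours". Neither mentions symptomatic drugs.

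Drug Information and Concomitant Medications/Treatments both prohibit only IL-6 inhibitors. Participants are outpatients, followed by phone and health-record review.

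In Appendix A, part A asks "Do you have a fever or feel feverish" and "Do you have muscle aches, pains, or cramps", each graded from absent to severe. Part B asks "What medication are you on currently" and records drug name, dose, frequency and whether the drug is newly started. It has no field for the last dose or the reason for use.

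Table 4 marks medication use at enrollment and for the two-day calls up to day 14. It does not mark it for the weekly calls, although the phone questionnaire is marked there.

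Section 14 compares the outcome (called TTCA there, read here as TTCR) by a two-sample t-test, with no rule for symptomatic drug use.

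**The concern.** Temperature and myalgia are the two TTCR components on which antipyretics and analgesics act directly. If a drug removes either for 72 hours and the other components have cleared, the definition gives a recovery date although the illness may still be active. The endpoint then measures a mixture of recovery and symptom control, and no analysis is planned that would separate them.

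Blinding does not make drug use equal between arms, because use follows symptoms. If RPS works, placebo participants would be ill for longer and have more reason to medicate. Their recorded recovery would be brought forward more, and the observed difference would shrink. What is at stake is the meaning and possible attenuation of one secondary estimate. The primary outcome, hospitalization, is not defined by these components.

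**Working it through.** **1. What the text permits**

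| Question | Where | Answer |
|---|---|---|
| Must the 72 hours be free of antipyretics or analgesics? | Secondary Outcome Measure; Section 1; Section 14 | No condition stated |
| Are such drugs barred? | Drug Information; Concomitant Medications/Treatments | No, only IL-6 inhibitors |
| Are current drugs asked about? | Appendix A, part B | Yes, without last dose or reason |
| Is this scheduled after day 14? | Table 4 | Questionnaire yes, medication use not marked |
| Are the answers used for TTCR? | Section 14 | No |

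**2. The plan's own figure**

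Inputs from Section 14: difference 2 days, SD 5 days, two-sided alpha 0.05, power 80%. Equal allocation is assumed, since no ratio is given.

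n per arm = 2 × (1.96 + 0.8416)² × 5² / 2² ≈ 98.1, so about 196 in total, or 198 after rounding each arm up to 99. The stated 196 reproduces.

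**3. How masking enters the difference**

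Let m_P and m_R be the mean days by which drug use brings forward the recorded recovery date in the placebo and RPS arms. Then

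observed difference = true difference − (m_P − m_R).

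Equal shifts shorten TTCR in both arms and leave the difference unchanged. Attenuation needs m_P > m_R. Each m is the share of participants whose date is moved times the mean days moved. The documents give neither, so the size cannot be computed.

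**4. Illustration only**

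Assume a true difference of 2 days and an SD that stays at 5. Power ≈ Φ(d / SE − 1.96), with SE = 5 × √(2/n).

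- At 98 per arm, SE = 5/7 = 0.714. For d = 1.8: 1.8/0.714 − 1.96 = 0.56, and Φ(0.56) = 71.2%.
- At 681 per arm (half of the 1362 that Section 14 requires), SE = 0.271. For d = 1.0: 1.0/0.271 − 1.96 = 1.73, and Φ(1.73) = 95.8%.

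| Assumed m_P − m_R (days) | Observed difference (days) | Power, 98 per arm | Total N for 80% | Power, 681 per arm |
|---|---|---|---|---|
| 0 | 2.0 | 80.0% | 198 | >99.9% |
| 0.2 | 1.8 | 71.2% | 244 | >99.9% |
| 0.5 | 1.5 | 55.6% | 350 | >99.9% |
| 1.0 | 1.0 | 28.8% | 786 | 95.8% |

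The exact t-test at 98 per arm gives almost the same values: 79.6% at 2.0 days and 70.8% at 1.8 days. The shifts in the first column are assumptions; nothing in the documents supports one over another.

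**The case against.** The strongest reply is that this is a legitimate choice. Counting recovery whatever permitted drugs are taken suits a home-based, patient-reported secondary outcome, and it fits the intention-to-treat principle that Section 14 states for the primary analysis. That stands as a reason to keep the current definition. It does not remove the need to say so, or to show how far the result depends on it.

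Second, the route is narrow. Cough, shortness of breath and GI symptoms must also clear, so a drug moves the date only where fever or myalgia would have been last. This stands.

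Third, a reader might infer that TTCR loses serious power. The low figures above belong to about 196 participants, not to the planned 1500. The interim analysis at about 200 does examine this outcome, but its only stated numerical stopping criterion concerns hospitalization. A reader might also infer that the comparison is shown to be biased. No document shows that masking occurs or differs between arms.

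Fourth, a drug-free rule cannot be derived reliably from the present script. Part B asks only what is being taken at the time of the call, so a drug stopped between calls may not be listed. This stands and shapes the fix.

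Fifth, the rule could add a distortion of its own. Analgesics taken for headache, which is not a TTCR symptom, or for abdominal cramps, which the protocol lists at 5–10% with starch, would delay recovery for reasons other than the infection. Cramps may differ by arm. This is why the stricter version should accompany the current one and not replace it.

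**Conclusion.** The point holds as a low-cost improvement in endpoint definition. As written, TTCR can record recovery in a participant whose fever or myalgia is only suppressed by permitted drugs, and the drug data from the call script play no part in it. Recorded times could be shortened. The difference between arms could be attenuated if masking is more common in the arm with the worse course. Both the amount and the arm imbalance are unknown from the documents.

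At planned enrollment the issue is validity, not power. That statement assumes 1:1 allocation, SD 5, and about 1362 participants with a usable TTCR.

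One further limit applies. Appendix A has no field for a measured temperature, so under this script a drug condition would in practice qualify an answer about feverishness.

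**What to change.** - Pre-specify a second TTCR version in which the 72-hour period contains no recorded antipyretic or analgesic use, except drugs unchanged since before enrollment for another condition. Report it alongside the current definition.
- Add to part B of Appendix A a short item on the date of last use of any such drug and the reason for it. Without this the second version is only approximate, and the exception cannot be applied.
- Mark medication use in Table 4 for the weekly calls. With a placebo mean of about 14 days assumed in Section 14, many recoveries may fall after day 14, where it is not now scheduled.
- Tabulate antipyretic and analgesic use by arm and by reason, so that use for headache or starch-related cramps can be seen.

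The cost is a few lines of endpoint text, one added script item, one schedule entry and a second derivation. Some recovery dates in the second version will be delayed by unrelated drug use, which is why both versions are shown. Participants called before the script changes will lack the new item. The change governs endpoint scoring only; it neither restricts nor recommends any drug.

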**Secondary Outcome Measure:**

Symptom severity score (2): This will be evaluated using a subjective self-reporting questionnaire (see section 15: Appendices) around eight symptoms, which include:

1) Shortness of breath at rest or on exertion

2) Fatigue

3) Myalgia/ muscle aches

4) Feverishness

5) Cough

6) Headaches

7) GI symptoms

8) Inability to taste or smell

Participants will rate each of their symptoms on an ordinal scale as follows:

absent (0), mild (1), moderate (2), or severe (3). These symptom ratings will be added to define the symptom severity score with a possible score range of 0–24 points.

Inquiry regarding symptom severity score will take place during phone questionnaires with patients performed Q2 days for 14 days from start of treatment then weekly until 30 days from last dose of treatment.

